6.4. Subset Analyses

The number of patients expected in each treatment group is small and therefore no subset analyses are planned in this study.

6.5. Baseline and Other Summaries and Analyses

6.5.1. Baseline Summaries

The following analyses will be based on the FAS overall and separately by treatment group.

6.5.1.1. Demographic Characteristics

Demographic characteristics and physical measurements will be summarized by treatment group using the following information from the ‘Screening/Baseline Visit’ eCRF pages.

- Demographic characteristics:
 - Gender: Male, Female;
 - Race: White, Black or African American, Asian, American Indian or Alaska Native, Native Hawaiian or other Pacific Islander, Other, Unknown;
 - Ethnic origin: Hispanic/Latino (‘Hispanic/Latino’, ‘Not Hispanic/Latino’, ‘Unspecified’);
 - Age (years): summary statistics;
 - Age categories:
 - <65 years, ≥65 years;
 - <65, 65-<75, 75-<85, ≥85 years.
 - Eastern Cooperative Oncology Group (ECOG) Performance Status: 0, 1, 2, 3, and 4.
- Physical measurements:
 - Height (cm);

- Weight (kg);
- Body Mass Index (BMI) (kg/m²);
- Body Surface Area (BSA) (m²).

The listing of demographics and baseline characteristics will include the following information: patient identifier, treatment group, age, sex, race, ethnicity, height (cm), weight (kg), BMI (kg/m²), BSA (m²) and ECOG performance status.

6.5.1.2. Medical History

Medical history will be coded using the most current available version of Medical Dictionary for Regulatory Activities (MedDRA) and will be summarized from the ‘Medical History’ eCRF page. Medical history will be summarized as the numbers and percentages of patients by MedDRA preferred term (PT) as event category and MedDRA primary system organ class (SOC) as summary category. Each patient will be counted only once within each PT or SOC.

Medical history will be displayed in terms of frequency tables: ordered by primary SOC and PT in alphabetical order.

6.5.1.3. Disease Characteristics

Information on disease characteristics collected on ‘Primary Diagnosis’ and RECIST eCRF pages will be summarized overall and by treatment group. Summary statistics will be presented for the following.

From the ‘Primary Diagnosis’ eCRF page:

- Primary diagnosis (summarize all categories collected in the ‘Primary Diagnosis’ eCRF page);
- Time since initial diagnosis to first dose of study treatment (months), defined as (first dose of study treatment – date of initial diagnosis)/30.4375;
- Time since diagnosis of local/regional recurrence of disease (months), defined as (first dose of study treatment – date of diagnosis of local/regional recurrence of disease or metastatic disease)/30.4375.

From the RECIST eCRF page:

- Measurable disease (lesions) at baseline (Yes, No);
- Involved tumor sites at baseline.

6.5.1.4. Prior Anti-cancer Therapies

The prior anti-cancer therapies are collected under the ‘Previous Systemic Therapy’, ‘Prior Radiation Therapy’ and ‘Prior Surgery’ eCRF pages.

The number and percentage of patients in each of the following anti-cancer therapy categories will be tabulated:

- Patients with at least one type of prior anti-cancer therapy;
- Patients with at least one prior anti-cancer drug therapy;
- Patients with at least one prior anti-cancer radiotherapy;
- Patients with at least one prior anti-cancer surgery.

Prior anti-cancer drug therapy will be summarized as follows based on the number and percentage of patients with the following:

- At least one prior anti-cancer drug therapy;
- Any prior anti-cancer drug therapy regimens: missing, 1, 2, 3, ≥ 4 ;
- Prior anti-cancer immune therapy (including PD-1, PD-L1, anti-CTLA4, others);
- Intent of Therapy: Neo-Adjuvant, Adjuvant, Advanced – Metastatic;
- Best response: CR, PR, SD, PD, Unknown, Not applicable (Adjuvant only). Best response is derived from the last treatment regimen.

The prior anti-cancer drug therapies will also be summarized based on the number and percentage of patients by the drug class and preferred term. A patient will be counted only once within a given drug class and within a given drug name, even if he/she received the same medication at different times. The summary will be sorted on decreasing frequency of drug class and decreasing frequency of drug name in a given drug class. In case of equal frequency regarding drug class (respectively drug name), alphabetical order will be used.

The listings of prior anti-cancer therapies will also be provided as follows. These will include the patient identification number, and all the relevant collected data-fields on the corresponding eCRF pages.

- Listing of prior anti-cancer drug therapies;
- Listing of prior anti-cancer radiotherapy;
- Listing of prior anti-cancer surgeries.

6.5.2. Study Conduct and Patient Disposition

The following analyses will be performed based on the FAS overall and separately by treatment group.

6.5.2.1. Patient Disposition

The percentages below will be calculated based on the number of patients in the FAS.

- Number and percentage of treated patients in each of the analysis sets defined in [Section 4](#);
- Number and percentage of patients with study drug ongoing (separately for each study drug when administered in combination);
- Number and percentage of patients who discontinued study drug overall and by the main reason for discontinuation of study drug (separately for each study drug when administered in combination);
- Number and percentage of patients who entered safety follow-up.

In addition the following will be summarized:

- Number and percentage of treated patients by center.

6.5.2.2. Protocol Deviations

All protocol violations that impact the safety of the patients and/or the conduct of a study and/or its evaluation will be reported. These include:

- Patients who are dosed on the study despite not satisfying the inclusion criteria;
- Patients who develop withdrawal criteria whilst on the study but are not withdrawn;
- Patients who receive the wrong treatment or an incorrect dose;
- Patients who receive an excluded concomitant medication;
- Deviations from GCP.

The identification of these and other CSR-reportable deviations will be based on the inclusion/exclusion criteria or other criteria presented in the protocol.

6.5.3. Study Treatment Compliance and Exposure

The following analyses will be based on the safety analysis set by treatment group.

All dosing calculations and summaries will be based on 'Dose_PF-05082566' and 'Dose_mogamulizumab' eCRFs pages. A listing of study drug administration will be created with the information collected on the 'Dose_PF-05082566' and 'Dose_mogamulizumab' eCRF pages.

Cycle definitions for study drugs that are administered in combination apply to all the study drugs in the combination. Ie, cycle is patient-dependent, rather than study-drug-dependent when study drugs are administered in combination.

For Cycle X, actual cycle start date for each patient is:

- the earliest start date of dosing in the Cycle X day 1 visit eCRF exposure page, if the patient received study treatment on that visit (ie, any study drug with dose>0 at that visit).
- the first day of assessments in the Cycle X day 1 visit, if the patient did not receive study treatment on that visit (ie, all study drugs had dose=0 at that visit). Use start date in the exposure page if available; if start date is not available then use date of collection of vital signs on Cycle X day 1 visit.

Actual cycle end date for each patient is,

- for all cycles X except the last cycle, actual cycle end date = actual cycle (X+1) start date – 1 day;
- for the last cycle, actual cycle end date = actual cycle start date + 28 days – 1 day.

Cycle duration (weeks) = (actual cycle end date – actual cycle start date + 1)/7.

When summarizing exposure for each study drug, only cycles from first dose of study treatment until the last cycle with non-zero dose of at least one of the study drugs should be included.

Exposure will be summarized (overall) as dose received (cumulative dose, actual dose intensity) and as dose received relative to intended dose (relative dose intensity [RDI]).

The formulae below should be applied to each study drug separately. In this study 1 cycle = 4 weeks.

The derivations below are provided for the following:

- PF-05082566 administered as a 1-hour IV infusion at a dose of 1.2 mg/kg, 2.4 mg/kg, 5 mg/kg, or 100 mg flat dose once every 4 weeks in 4-week cycles.
- Mogamulizumab will be administered as a 1-hour IV infusion at a dose of 1 mg/kg or 0.5 mg/kg weekly for 4 consecutive weeks in the first cycle (ie, on Days 1, 8, 15 and 22), followed by biweekly dosing in cycles ≥ 2 (ie, on Days 1 and 15).

Analysis of exposure will be based on the calculated actual dose levels:

- PF-05082566: total dose / weight, or total dose (for the flat dose cohort);
- Mogamulizumab: total dose / weight.

6.5.3.1. Exposure to PF-05082566

For weight-adjusted dose:

The dose level for PF-05082566 is calculated as actual dose administered/weight (mg/kg). The last available weight of the patient on or prior to the day of dosing will be used.

Intended duration of treatment with PF-05082566 (weeks) =

$$(\text{end date} - \text{date of first dose of PF-05082566} + 1)/7,$$

where end date = start date of last cycle with non-zero dose of PF-05082566 + 28 – 1

Duration of exposure to PF-05082566 (weeks) =

$$(\text{last dose date of PF-05082566} - \text{first dose date of PF-05082566} + 28)/7$$

Cumulative dose overall is the sum of the actual doses of PF-05082566 received overall.

Each cycle for PF-05082566 is defined by a 4-week period. The dose intensity (DI) and the relative dose intensity (RDI) will be calculated for each patient across all cycles.

Actual Dose Intensity (DI)

- Overall actual DI (mg/kg/4-week cycle) = [overall cumulative dose (mg/kg)] / [intended duration of treatment with PF-05082566 (weeks)/4].

Relative Dose Intensity (RDI)

- Intended DI (mg/kg/4-week cycle) = [intended cumulative dose per cycle] / [intended number of 4-weeks in a cycle] = [d (mg/kg)] / [1 (4-week cycle)] = d (mg/kg/4-week cycle).
- Overall RDI (%) = $100 \times [\text{overall actual DI}] / [\text{intended DI}]$
 $= 100 \times [\text{overall actual DI}] / [d (\text{mg/kg/4-week cycle})]$.

where d is 1.2 mg/kg, 2.4 mg/kg, or 5 mg/kg.

The summary of treatment exposure and compliance for PF-05082566 will include the following information:

- Treatment duration (weeks);
- Total number of infusions received;
- Cumulative dose (mg/kg);
- Dose intensity (mg/kg/cycle);

- Relative dose intensity (%).

For flat dose:

The dose level for PF-05082566 is calculated as actual dose administered (mg).

Intended duration of treatment with PF-05082566 (weeks) =

$$(\text{end date} - \text{date of first dose of PF-05082566} + 1)/7,$$

where end date = start date of last cycle with non-zero dose of PF-05082566 + 28 – 1

Duration of exposure to PF-05082566 (weeks) =

$$(\text{last dose date of PF-05082566} - \text{first dose date of PF-05082566} + 28)/7$$

Cumulative dose overall is the sum of the actual doses of PF-05082566 received overall.

Each cycle for PF-05082566 is defined by a 4-week period. The dose intensity (DI) and the relative dose intensity (RDI) will be calculated for each patient across all cycles.

Actual Dose Intensity (DI)

- Overall actual DI (mg/4-week cycle) = [overall cumulative dose (mg)] / [intended duration of treatment with PF-05082566 (weeks)/4].

Relative Dose Intensity (RDI)

- Intended DI (mg/4-week cycle) = [intended cumulative dose per cycle] / [intended number of 4-weeks in a cycle] = [100 (mg)] / [1 (4-week cycle)] = 100 (mg/4-week cycle).
- Overall RDI (%) = $100 \times [\text{overall actual DI}] / [\text{intended DI}]$
 $= 100 \times [\text{overall actual DI}] / [100 (\text{mg/4-week cycle})]$.

The summary of treatment exposure and compliance for PF-05082566 will include the following information:

- Treatment duration (weeks);
- Total number of infusions received;
- Cumulative dose (mg);
- Dose intensity (mg/cycle);
- Relative dose intensity (%).

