6.5.3.2. Exposure to Mogamulizumab

The dose level for mogamulizumab is calculated as actual dose administered/weight (mg/kg). The last available weight of the patient on or prior to the day of dosing will be used.

Intended duration of treatment with mogamulizumab (weeks) =

$$(\text{end date} - \text{date of first dose of mogamulizumab} + 1)/7,$$

where end date = start date of last cycle with non-zero dose of mogamulizumab + 28 – 1.

Duration of exposure to mogamulizumab (weeks) =

$$(\text{last dose date of PF-05082566} - \text{first dose date of PF-05082566} + d)/7$$

where d is 7 days if the last dose is in Cycle 1 and 14 days if the last dose is beyond Cycle 1.

Cumulative dose overall is the sum of the actual doses of mogamulizumab received overall.

Each cycle for mogamulizumab is defined by a 4-week period. The dose intensity (DI) and the relative dose intensity (RDI) will be calculated for each patient across all cycles.

Actual Dose Intensity (DI)

- Overall actual DI (mg/kg/4-week cycle) = [overall cumulative dose (mg/kg)] / [intended duration of treatment with mogamulizumab (weeks)/4].

Relative Dose Intensity (RDI)

- For patients that discontinued mogamulizumab before C2D1, then
 - Intended DI (mg/kg/4-week cycle) = [intended cumulative dose per cycle] / [intended number of 4-weeks in a cycle] = $[4 \times d \text{ mg/kg}] / [1 \text{ (4-week cycle)}] = 4 \times d \text{ (mg/kg/4-week cycle)}$.
 - Overall RDI (%) = $100 \times [\text{overall actual DI}] / [\text{intended DI}] = 100 \times [\text{overall actual DI}] / [4 \times d \text{ (mg/kg/4-week cycle)}]$

where d is 1 or 0.5.

- For patients that were treated with mogamulizumab beyond C2D1, then
 - Intended DI (mg/kg/4-week cycle).
$$= [(n_1 \times 4 \times d \text{ (mg/kg)} + n_2 \times 4 \times d/2 \text{ (mg/kg)}) / (n_1 + n_2)] / [\text{intended number of 4-weeks in a cycle}]$$
$$= [(n_1 \times 4 \times d \text{ (mg/kg)} + n_2 \times 4 \times d/2 \text{ (mg/kg)}) / (n_1 + n_2)] / [1 \text{ (4-week cycle)}]$$

$$= [(n_1 \times 4 \times d + n_2 \times 4 \times d/2) / (n_1 + n_2)] \text{ (mg/kg/4-week cycle)}$$

where,

- $n_1 = 1$
- $n_2 = \text{intended duration of treatment with mogamulizumab (weeks)}/4 - n_1$
- $n_1 + n_2 = \text{intended duration of treatment with mogamulizumab (weeks)}/4$
- d is 1 or 0.5.
- Overall RDI (%) = $100 \times [\text{overall actual DI}] / [\text{intended DI}]$.

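### SAP 6.5.3 and the formulas in 6.5.3.1 and 6.5.3.2 end the relative-dose-intensity window at different cycles, so RDI is ambiguous for a patient who stops one drug and continues the other

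*SAP*

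**What the plan says.** SAP 6.5.3 (Study Treatment Compliance and Exposure) sets the general rules. A cycle belongs to the patient: "cycle is patient-dependent, rather than study-drug-dependent when study drugs are administered in combination". When exposure is summarised for each drug, the cycles run "until the last cycle with non-zero dose of at least one of the study drugs should be included". The next sentence lists what is summarised: "Exposure will be summarized (overall) as dose received (cumulative dose, actual dose intensity) and as dose received relative to intended dose", that is, RDI. The section then directs the reader to apply the formulas that follow to each drug separately.

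SAP 6.5.3.1 computes actual DI for PF-05082566 as cumulative dose divided by an intended duration in 4-week units. That duration stops at a date defined by this drug alone: "where end date = start date of last cycle with non-zero dose of PF-05082566 + 28" days less one. The weight-based and flat-dose versions share this end date. SAP 6.5.3.2 uses the parallel rule for mogamulizumab: "where end date = start date of last cycle with non-zero dose of mogamulizumab + 28 – 1". Both subsections also state that DI and RDI are taken over all cycles.

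For mogamulizumab the intended DI has two branches. One begins "For patients that discontinued mogamulizumab before C2D1, then" and uses 4d per cycle, where d is the dose per infusion. The other, for patients treated beyond that visit, averages one cycle at 4d and n2 cycles at 2d.

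**The concern.** The general section and the formulas give different end points for the same quantity, and no text says which governs once one drug has stopped. Two programmers could each follow the SAP and produce different tables.

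The SAP expects the situation. Section 6.5.2.1 tabulates discontinuation, with its main reason, separately for each drug. Section 6.6.1.2 tabulates adverse events leading to discontinuation of each drug. Protocol 5.4.8 contemplates resuming one or both drugs after a hold.

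At stake is how the exposure tables read. Under the formulas, a drug stopped after one full cycle can appear with an RDI of 100% while the patient stays on study treatment for many more cycles with the other drug. The neighbouring summaries do not pick up the missing doses: 6.5.3.3 counts reductions among non-zero doses, and 6.5.3.4 measures delay between consecutive non-zero doses. Doses never given after the last one enter neither.

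**Working it through.** The documents print no RDI value, so there is no figure to reproduce. The check applies the SAP formula under each window.

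**Inputs**
- Cycle length 4 weeks (SAP 6.5.3); about 24 cycles at most (SAP 2.2).
- PF-05082566: one dose d per cycle (SAP 6.5.3.1).
- Mogamulizumab: four doses of d in Cycle 1, two per cycle afterwards (SAP 6.5.3.2).
- Assumed, not in the documents: the stopped drug is given in the first k cycles, the other drug continues to cycle T, doses are full and there are no delays.

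**Formula**

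RDI = 100 × [cumulative dose ÷ (intended duration in weeks ÷ 4)] ÷ intended DI

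**PF-05082566**
- Cumulative dose = k·d; intended DI = d per cycle.
- Drug-specific window: duration ÷ 4 = k, so RDI = 100 × k/k = 100% for every k.
- Either-drug window: duration ÷ 4 = T, so RDI = 100 × k/T.

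**Mogamulizumab**
- Cumulative dose = d[4 + 2(k − 1)].
- Drug-specific window: intended cumulative dose is the same expression, so RDI = 100%.
- Either-drug window with the cycle-weighted intended dose: RDI = 100 × [4 + 2(k − 1)] ÷ [4 + 2(T − 1)]. For T = 6 the denominator is 4 + 5 × 2 = 14.

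**Results for T = 6**

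| k | Either drug, own window | PF-05082566, either-drug window | Mogamulizumab, either-drug window |
|---|---|---|---|
| 1 | 100% | 1/6 = 16.7% | 4/14 = 28.6% |
| 2 | 100% | 2/6 = 33.3% | 6/14 = 42.9% |
| 3 | 100% | 3/6 = 50.0% | 8/14 = 57.1% |
| 5 | 100% | 5/6 = 83.3% | 12/14 = 85.7% |

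The mogamulizumab figure for k = 1 depends on the branch. If the window is lengthened but the SAP's early-stop branch is kept, intended DI stays at 4d for all six cycles and RDI = 100 × (4/6) ÷ 4 = 16.7%, not 28.6%. The window and the branch must therefore be settled together.

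**Range.** For T from 2 to 24, the PF-05082566 value under the either-drug window runs from 1/24 = 4.2% to 23/24 = 95.8%.

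**Where the windows do not differ.** If both drugs have their last dose in the same cycle, k = T and the two results coincide. A cycle withheld and then followed by resumption is also handled: PF-05082566 in Cycles 1, 2 and 4 with Cycle 3 held gives 3/4 = 75% under the formula in 6.5.3.1. Only cycles after the drug's last dose fall outside.

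**Where 100% does not hold.** Three PF-05082566 doses with one 7-day delay give 3 ÷ [(84 + 7)/28] = 3 ÷ 3.25 = 92.3% under the drug-specific window.

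**The case against.** The best defence is that 6.5.3 contains no RDI formula. Its sentence limits which cycles may enter, and the formulas, applied drug by drug, then name explicit end dates. On that view the only computable RDI uses the drug's own window, and intensity while on the drug is a legitimate measure. The last part stands. The rest does not dispose of the conflict. If the general sentence is only an outer bound, it changes none of the listed overall summaries, because cycles without the drug add nothing to cumulative dose or infusion count and the durations have their own formulas. The sentence has an effect only if it sets the DI and RDI denominator.

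A second objection is that the protocol hardly describes mogamulizumab continuing without PF-05082566. Protocol 5.4 defines a cycle by successive PF-05082566 doses, and Table 8 acts on both drugs or on mogamulizumab only. That bears on how often the case arises, and the frequency is unknown. SAP 6.5.3 nevertheless starts a cycle when any study drug is given at the Day 1 visit, so its rules do cover the case.

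A third objection is that early stopping of one drug is visible elsewhere: in the per-drug discontinuation tables (6.5.2.1, 6.6.1.2) and in the infusion counts and cumulative doses beside RDI. This is correct and limits the harm.

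A reader might infer four stronger things that the documents do not support:
- That the formulas ignore every withheld cycle. They ignore only those after the last dose of that drug.
- That RDI is the SAP's sole comparison of actual with planned dosing. Sections 6.5.3.3 and 6.5.3.4 also make such comparisons.
- That any patient losing a drug to toxicity would show 100%. Earlier reductions, omissions or delays lower the figure under the formulas too.
- That dose selection is compromised. Protocol 3.6 links the RP2D to feasibility of long-term administration, but mentions neither RDI nor a threshold for it.

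**Conclusion.** The SAP states two conflicting windows for DI and RDI, and they should be reconciled. The difference arises only for patients who stop one drug permanently while the other continues into later cycles. For them the gap can be anything from small to nearly the whole scale, depending on when the drug stops and how long the other continues. The percentages shown rest on full doses and no delays and are not predictions. How many patients would be affected cannot be judged from the documents.

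The consequence is confined to descriptive exposure and compliance tables, where RDI could read as full intensity for a drug stopped early. DLT and MTD analyses do not use RDI. This is a correction worth making before the tables are programmed; it does not threaten the trial's conclusions.

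**What to change.** Use one DI and RDI window in 6.5.3, 6.5.3.1 (weight-based and flat dose) and 6.5.3.2. Following the SAP's general rule:

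- End date for either drug = first day of the last cycle in which at least one study drug was given at a non-zero dose, + 28 − 1.
- Mogamulizumab: whenever either drug was given beyond Cycle 1, intended cumulative dose = 4d + 2d × n2, with n2 the number of 4-week units in that window after the first. Keep the early-stop branch only for patients who received neither drug beyond Cycle 1.
- Report the drug-specific calculation as a separate row labelled *RDI while on the drug*, so that both readings are available and cannot be confused.

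The cost is a change of SAP wording and slightly more programming. Reported RDI will be lower for patients who stop one drug early. Section 6.5.3.2 needs an edit in any case, because its formula for duration of exposure to mogamulizumab is written with PF-05082566 dose dates.

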6.5.3.2. Exposure to Mogamulizumab

The dose level for mogamulizumab is calculated as actual dose administered/weight (mg/kg). The last available weight of the patient on or prior to the day of dosing will be used.

Intended duration of treatment with mogamulizumab (weeks) =

$$(\text{end date} - \text{date of first dose of mogamulizumab} + 1)/7,$$

where end date = start date of last cycle with non-zero dose of mogamulizumab + 28 – 1.

Duration of exposure to mogamulizumab (weeks) =

$$(\text{last dose date of PF-05082566} - \text{first dose date of PF-05082566} + d)/7$$

where d is 7 days if the last dose is in Cycle 1 and 14 days if the last dose is beyond Cycle 1.

Cumulative dose overall is the sum of the actual doses of mogamulizumab received overall.

Each cycle for mogamulizumab is defined by a 4-week period. The dose intensity (DI) and the relative dose intensity (RDI) will be calculated for each patient across all cycles.

Actual Dose Intensity (DI)

- Overall actual DI (mg/kg/4-week cycle) = [overall cumulative dose (mg/kg)] / [intended duration of treatment with mogamulizumab (weeks)/4].

Relative Dose Intensity (RDI)

- For patients that discontinued mogamulizumab before C2D1, then
 - Intended DI (mg/kg/4-week cycle) = [intended cumulative dose per cycle] / [intended number of 4-weeks in a cycle] = $[4 \times d \text{ mg/kg}] / [1 \text{ (4-week cycle)}] = 4 \times d \text{ (mg/kg/4-week cycle)}$.
 - Overall RDI (%) = $100 \times [\text{overall actual DI}] / [\text{intended DI}] = 100 \times [\text{overall actual DI}] / [4 \times d \text{ (mg/kg/4-week cycle)}]$

where d is 1 or 0.5.

- For patients that were treated with mogamulizumab beyond C2D1, then
 - Intended DI (mg/kg/4-week cycle).
$$= [(n_1 \times 4 \times d \text{ (mg/kg)} + n_2 \times 4 \times d/2 \text{ (mg/kg)}) / (n_1 + n_2)] / [\text{intended number of 4-weeks in a cycle}]$$
$$= [(n_1 \times 4 \times d \text{ (mg/kg)} + n_2 \times 4 \times d/2 \text{ (mg/kg)}) / (n_1 + n_2)] / [1 \text{ (4-week cycle)}]$$

$$= [(n_1 \times 4 \times d + n_2 \times 4 \times d/2) / (n_1 + n_2)] \text{ (mg/kg/4-week cycle)}$$

where,

- $n_1 = 1$
- $n_2 = \text{intended duration of treatment with mogamulizumab (weeks)}/4 - n_1$
- $n_1 + n_2 = \text{intended duration of treatment with mogamulizumab (weeks)}/4$
- d is 1 or 0.5.
- Overall RDI (%) = $100 \times [\text{overall actual DI}] / [\text{intended DI}]$.

The summary of treatment exposure and compliance for mogamulizumab will include the following information:

- Treatment duration (weeks);
- Total number of infusions received;
- Cumulative dose (mg/kg);
- Dose intensity (mg/kg/cycle);
- Relative dose intensity (%).

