3.4. Baseline Variables

3.4.1. Study Drug, Study Treatment and Baseline Definitions

In this study, ‘study drug’ refers to PF-05082566 or mogamulizumab and ‘study treatment’ (or ‘treatment group’) refers to one of the following:

- Dose Level -1: PF-05082566 1.2 mg/kg q4wks + mogamulizumab 0.5 mg/kg;
- Dose Level 1: PF-05082566 1.2 mg/kg q4wks + mogamulizumab 1 mg/kg;
- Dose Level 1a: PF-05082566 100 mg q4wks + mogamulizumab 1 mg/kg;
- Dose Level 2: PF-05082566 2.4 mg/kg q4wks + mogamulizumab 1 mg/kg;
- Dose Level 3: PF-05082566 5 mg/kg q4wks + mogamulizumab 1 mg/kg.

Start and end dates of study treatment:

The date/time of first dose of study treatment is the earliest date/time of the first non-zero dose date/time for the study drugs in the combination.

The date/time of last dose of study treatment is the latest date/time of the last non-zero dose date/time for the study drugs in the combination.

Definition of baseline:

The last available assessment prior to the start of study treatment is defined as ‘baseline’ value or ‘baseline’ assessment for safety and efficacy analyses. If an assessment is planned to be performed prior to the first dose of study treatment in the protocol and the assessment is performed on the same day as the first dose of study treatment, it will be assumed that it was performed prior to study treatment administration, if assessment time point is not collected or is missing. If assessment time points are collected, the observed time point will be used to determine pre-dose on study day 1 for baseline calculation. Unscheduled assessments will be used in the determination of baseline. However, if time is missing, an unscheduled assessment on study day 1 will be considered to have been obtained after study treatment administration.

Patients who start treatment and discontinue from the study on the same day may have two different sets of data collected on study day 1 (one during study and one in the End of Treatment (EOT) visit. Data reported at the EOT visit are not eligible for baseline selection.

If a scheduled pre-dose measurement actually occurred post-dose, then the corresponding measurement will be treated and analyzed similar to an unscheduled post-dose measurement.

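### The mogamulizumab duration-of-exposure formula uses PF-05082566 dose dates, so it comes out too short or too long unless both drugs' last doses fall on the same Day 1

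*SAP*

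**What the plan says.** SAP Section 6.5.3 introduces the exposure derivations with the instruction "The formulae below should be applied to each study drug separately".

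Section 6.5.3.2 then gives two durations for mogamulizumab:

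- **Intended duration**, which runs from the first mogamulizumab dose to an end date built on mogamulizumab: "where end date = start date of last cycle with non-zero dose of mogamulizumab + 28" days, less 1.
- **Duration of exposure**, headed "Duration of exposure to mogamulizumab (weeks". Its numerator is the last PF-05082566 dose date minus the first PF-05082566 dose date, plus d. The end of the formula reads "first dose date of PF-05082566} + d)/7" (the stray bracket comes from reading the PDF). The add-on is defined by "where d is 7 days if the last dose is in Cycle 1 and 14 days if the last dose is beyond Cycle 1".

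The summary list that closes the section contains the line "Treatment duration (weeks" without saying which of the two durations it reports.

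**The concern.** The exposure formula combines one drug's dates with the other drug's dosing interval. A 7-day then 14-day add-on matches weekly then biweekly mogamulizumab. The PF-05082566 formula in Section 6.5.3.1 uses the same PF-05082566 dates with an add-on of 28. The likely explanation is that the dates were carried over from 6.5.3.1 and only the add-on was changed.

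Two smaller gaps go with it. The last dose that sets d is not tied to a drug, which matters when one drug stops in Cycle 1 and the other later. And the summary label could mean either duration.

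At stake is a descriptive statement of how long patients were exposed to mogamulizumab. If the summary line is the duration of exposure, it will be wrong for identifiable groups of patients. If it is the intended duration, the table is right, and the SAP carries a wrong formula that feeds no listed output.

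**Working it through.** The SAP gives a formula here but no figure, so there is none to reproduce. The check applies the formula to the planned schedule and compares it with the same formula on mogamulizumab dates.

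**Inputs**

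- PF-05082566: Day 1 of each 28-day cycle (Protocol 3.1.3 and 5.4.1; SAP 2.2).
- Mogamulizumab: Days 1, 8, 15 and 22 of Cycle 1, then Days 1 and 15 of each later cycle (Protocol 5.4.2; SAP 2.2).
- Both first doses on Cycle 1 Day 1 and no delays, as scheduled. Day x of cycle c is then study day 28(c − 1) + x.
- d = 7 if the last dose is in Cycle 1, otherwise 14.

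**Formulae**

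- As written: (last PF-05082566 day − 1 + d)/7
- With mogamulizumab dates: (last mogamulizumab day − 1 + d)/7

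**Both drugs stop in the same cycle**

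| Last mogamulizumab dose | As written (weeks) | Mogamulizumab dates (weeks) | Error |
|---|---|---|---|
| C1 D1 | (0+7)/7 = 1 | (0+7)/7 = 1 | 0 |
| C1 D8 | 1 | (7+7)/7 = 2 | −1 |
| C1 D15 | 1 | (14+7)/7 = 3 | −2 |
| C1 D22 | 1 | (21+7)/7 = 4 | −3 (−75%) |
| C2 D1 | (28+14)/7 = 6 | 6 | 0 |
| C2 D15 | 6 | (42+14)/7 = 8 | −2 (−25%) |
| C6 D15 | (140+14)/7 = 22 | (154+14)/7 = 24 | −2 (−8%) |
| C24 D15 | (644+14)/7 = 94 | (658+14)/7 = 96 | −2 (−2%) |

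The SAP's own intended duration supports the right-hand column. For a patient who receives the last planned dose of cycle c it is 28c/7 = 4c weeks, that is 4, 8, 24 and 96 weeks for Cycles 1, 2, 6 and 24. These equal the values on mogamulizumab dates, not those from the formula as written.

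Over 24 cycles there are 4 + 23 × 2 = 50 scheduled positions for the last mogamulizumab dose. The formula is exact at the 24 Day 1 positions and too short at the other 26 (3 in Cycle 1, 23 later). These are calendar positions, not patients; the documents give no distribution of stopping times.

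**The drugs stop in different cycles (illustrations)**

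| Last PF-05082566 | Last mogamulizumab | As written (weeks) | Mogamulizumab dates (weeks) |
|---|---|---|---|
| C2 D1 | C4 D15 | (28+14)/7 = 6 | (98+14)/7 = 16 |
| C4 D1 | C2 D15 | (84+14)/7 = 14 | (42+14)/7 = 8 |
| C2 D1 | C1 D22 | (28+7)/7 = 5 or (28+14)/7 = 6 | (21+7)/7 = 4 |

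The last row shows the effect of leaving d undefined. The result is 5 or 6 weeks according to whose last dose sets d, and neither is right.

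**The case against.** The wrong drug name cannot be defended. Nothing elsewhere in the SAP corrects it, and both date terms name PF-05082566 in full. The case on the other side concerns reach and wording.

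- **The impact may be nil.** If the summary line means the intended duration, no listed output changes, and the instruction to treat each drug separately would lead an alert programmer to the right dates. This stands as a limit on severity. It does not make the formula right.
- **Different-cycle stops are thinly supported.** Protocol 5.4.4 speaks of continuing on both agents, and Protocol 5.4 defines a cycle by successive PF-05082566 Day 1 doses. Against that, SAP 6.5.2.1 counts discontinuation "separately for each study drug when administered in combination", SAP 6.6.1.2 tabulates adverse events leading to discontinuation of each drug, and Protocol 5.4.8 lets either or both drugs resume. Separate stopping is foreseen, but its frequency is unknown, so those rows are illustrations. The same-cycle shortfalls do not depend on them.
- **The condition for exactness is incomplete.** It also needs the first doses to coincide. If mogamulizumab started on C1 D8 and both last doses fell on C3 D1, the formula would give (56+14)/7 = 10 weeks against (49+14)/7 = 9. This is correct, but both first doses are scheduled for C1 D1.
- **The count of 50 treats approximately 24 cycles as exactly 24.** On the SAP's 104 weeks (26 cycles) it would be 4 + 25 × 2 = 54 positions, 26 of them exact. Either way, the count says nothing about numbers of patients.
- **The unnamed drug in d follows from the main error.** Under a mogamulizumab heading, the natural reading is the mogamulizumab dose. That is fair once the dates are corrected, but saying so costs one word.
- **The undefined label also appears in both PF-05082566 lists in 6.5.3.1.** This is right, and the fix should cover them for consistency.

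**Conclusion.** The formula is wrong as written. On the planned schedule, with both drugs stopping in the same cycle, it understates mogamulizumab exposure whenever the last mogamulizumab dose comes after Day 1 of that cycle: by 1 to 3 weeks in Cycle 1 and by 2 weeks later. If mogamulizumab stops in an earlier cycle than PF-05082566, it can overstate exposure. It is exact when both last doses fall on the same Day 1. These results assume 28-day cycles, no delays and both first doses on Cycle 1 Day 1. How many patients would be affected cannot be derived from the documents.

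Severity is minor. Cumulative dose and number of infusions do not use this formula, and dose intensity and relative dose intensity use the intended duration. The on-treatment period, and so the adverse event summaries, rests on a rule covering both drugs: "The date/time of last dose of study treatment is the latest date/time of the last non-zero dose date/time for the study drugs" in the combination. DLTs and the MTD are untouched.

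**What to change.** In SAP Section 6.5.3.2:

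1. Change the formula to (last dose date of mogamulizumab − first dose date of mogamulizumab + d)/7.
2. State that d is 7 days if the last mogamulizumab dose is in Cycle 1 and 14 days if it is later.
3. In the summary list, replace the treatment-duration label with the name of the duration actually reported. Do the same in the two PF-05082566 lists in Section 6.5.3.1 so that all three agree.

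The cost is a one-line formula correction, one clarifying word for d, one label in each of three lists and one programming line. No data collection, dose or schedule changes.
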